4.5 Secondary outcome analyses

Engagement with SSS will be analysed using a mixed-effects logistic regression model adjusting for treatment group, age, years of smoking, income status, level of smoking (as measured by the Fagerström score) and whether the engagement data was collected before the 16th of March 2020, with centre as a random effect.

CO-validated smoking status at 4 weeks post-quit date will be analysed using a mixedeffects logistic regression model, adjusting for treatment group, age, years of smoking, income status, level of smoking (as measured by the Fagerström score) and whether the CO-validated smoking status was collected before the 16th of March 2020, with centre as a random effect. If a participant is missing their smoking status, it shall be assumed the participant is smoking.

Birth weight will be analysed using a mixed-effects linear regression model, adjusting for treatment group, the age, height and weight of the mother at booking, years of smoking, income status, level of smoking (as measured by the Fagerström score) and whether the birthweight data was collected before the 16th of March 2020 as fixed effects, and centre as a random effect. If a participant is missing data on birth weight, it shall be assumed the data is missing at random conditional on the covariates included in the analysis model [13, 14].

Continuous and point abstinence outcomes obtained at six months postpartum will be analysed using mixed-effects logistic regression adjusting for the same covariates and applying the same assumptions used in the primary outcome analysis (with the exception that whether the postpartum point abstinence outcome was collected before 16th of March 2020 will be adjusted for instead of adjusting for whether the primary outcome was collected before the 16th of March 2020). If a participant is missing their smoking status, it shall be assumed the participant is smoking. Participants who at postpartum were followed up earlier than 6 months will be excluded from the analysis of continuous and point abstinence

outcomes obtained at six months postpartum, and will be accounted for in a sensitivity analysis.

4.6 Exploratory outcome analysis

Length of neonatal stay will be summarised descriptively by treatment group.

4.7 Sensitivity analyses

4.7.1 Sensitivity of primary analysis to sparse data bias

To assess the sensitivity of the primary analysis to sparse data bias, the primary outcome will be analysed using a Firth logistic regression model adjusting for treatment group, age, years of smoking, income status (as measured by IMD score), level of smoking (as measured by the Fagerström score), whether the primary outcome was collected before the 16th of March 2020 and site [11]. All variables will be adjusted for as fixed effects, as the Stata command used to implement Firth logistic regression cannot incorporate random effects.

4.7.2 Impact of the Covid-19 pandemic on analysis of the primary and secondary smoking outcomes

To assess the impact of the Covid-19 pandemic on the primary and secondary smoking outcomes, the number of self-reported non-smokers pre-Covid and post-Covid will be compared descriptively by treatment group (Table 6). This will allow assessment of the possibility that participants in the incentives group were more likely to report as non-smokers to receive financial incentives post-Covid compared to pre-Covid. In addition, the number of participants who self-reported as non-smokers but provided a positive biochemical sample pre-Covid and post-Covid will be compared descriptively by treatment group (Table 7).

The number of biochemically verified non-smokers pre-Covid and post-Covid will also be compared descriptively by treatment group (Table 8), in order to assess the possibility that the treatment effect pre-Covid is different to the treatment effect post-Covid.

If the above checks indicate the Covid-19 pandemic had an impact on the analysis of the primary and secondary smoking outcomes, the analyses of these outcomes shall be repeated with the addition of an interaction term between treatment allocation and a pre-Covid/post-Covid variable, with effect size estimates pre-Covid and post-Covid presented alongside corresponding 95% confidence intervals and p-values.

Finally, in order to assess whether the change in intervention had an impact on the return of biochemical samples, the number of returned biochemical samples pre-Covid and post-Covid will be compared descriptively by treatment group in the subset of self-reported non-smokers (Table 9).

4.7.3 Subgroup analyses

The primary analysis will be repeated, with the addition of interaction terms between treatment group and each of the following covariates:

- Maternal age (≤28 years vs >28 years, with 28 years being the mean age of a first time mother according to the ONS in 2015)
- Index of multiple deprivation quintile (1/2/3/4/5)
- Years of smoking (≤10 years vs >10 years)
- Fagerström score (the cut-off will be decided using data on the distribution of the Fagerström score in the previous CPIT RCT)

4.7.4 Missing data analyses

If a participant is missing data on the primary outcome, the participant shall be assumed to be smoking, as per the Russell Standard [9]. The robustness of the primary analysis to this assumption will be explored using two methods.

The first method will use multiple imputation by chained equations [15]. Missing values of baseline covariates will be replaced with centre-specific means. The imputation model for the biochemically verified smoking status at late pregnancy will include the baseline covariates used in the primary analysis, the treatment allocation, engagement with SSS, CO-validated smoking status at 4 weeks post-quit and biochemically verified point abstinence at 6 months post-partum.

Each imputed dataset will be analysed using the primary analysis model. The estimates obtained from analysis of the imputed datasets will then be combined using Rubin's rules.

The second method will explore the sensitivity of the results to the missing data mechanism using a pattern mixture model, which will be implemented using the <code>rctmiss</code> command in Stata [16]. The pattern mixture model expresses assumptions about the missing data mechanism in the form of a logistic regression model regressing the outcome on a set of covariates and a missing data indicator, whose parameter shall be denoted as β_m . The Russell standard is equivalent to assuming that $\beta_m = -\infty$ i.e. missing=non-quitter. Negative values of β_m assume that participants with missing smoking status are less likely to have quit than participants with non-missing smoking status, while positive values assume that participants with non-missing smoking status are more likely to have quit than participants with missing smoking status. The consequences of varying β_m over a range of values shall be explored and displayed graphically.

4.7.5 Impact of participants who were followed up at postpartum earlier than the planned 6 months

The number and proportion of participants who were followed up earlier than 6 months postpartum will be summarised descriptively by trial arm. The time in months between the planned follow-up date and actual follow-up date will be summarised descriptively by trial arm.

Participants who provide a smoking status postpartum will be grouped by whether the postpartum follow-up took place between:

- Less than two months postpartum
- More than or equal to two months postpartum and less than four months postpartum
- More than or equal to four months postpartum and less than six months postpartum
- More than or equal to six months postpartum

Within these groups, the number and proportion of participants who were cotinine/anabasine validated non-smokers will be summarised descriptively.

4.7.6 Sensitivity of primary analysis to assumption regarding participants with missing anabasine test

In the primary analysis it will be assumed that for those participants who provided a biochemical sample but due to a miscommunication with the lab were not tested for anabasine, that if they have a CO reading less than 4 ppm then they are non-smokers. The impact of this assumption on the primary analysis will be explored by repeating the primary analysis under two different scenarios. The first scenario will assume that the participants in the incentives group were smokers while the participants in the control group were non-

smokers. The second scenario will assume the participants in the incentives group were non-smokers while the participants in the control group were smokers.

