2.3.2 Changes to the intervention in response to the Covid-19 pandemic

Due to the Covid-19 pandemic, SSS were disrupted. As a result, on the 16th of March 2020 the following changes were made for the intervention group:

- Participants who received SSS behavioural support and set a quit date via telephone (where this would have previously been conducted face-to-face) were considered to have engaged with the SSS, and received a gift voucher with the value of £50.
- Participants who self-reported as having quit with no CO verification at the 4-week follow-up received a gift voucher with the value of £50.
- Participants who self-reported as having quit at the 4-week follow-up were contacted at the 12 week follow-up. If they self-reported as quit with no CO verification at the 12-week follow-up they were sent a gift voucher with the value of £100.
- Participants who self-reported as having quit at the primary outcome stage in late pregnancy and for whom a saliva sample was received by the trial team were sent a gift voucher with the value of £200.

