2.6 Sample size

The aim was to recruit 940 participants to the trial (470 per arm). This gave 90% power to detect a doubling of the smoking cessation rate from 7% to 14%, allowing 15% loss to follow-up. The smoking cessation rate in the control group was derived from the smoking cessation rate found in the feasibility trial [2], and two other large trials of smoking cessation interventions in pregnant smokers [3, 4]. The smoking cessation rate in the intervention group was derived from the cessation rate in the feasibility trial, along with considerations of the effect size that would be considered clinically important.

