4.1 Strategy for reporting data and general considerations

Data will be analysed and reported according to CONSORT guidelines [5]. A CONSORT diagram will be produced (see Figure 2). Analyses will be conducted using Stata version 16 or later [6]. The version of Stata to be used will be confirmed in the final report. All analyses will be conducted following the principle of intention-to-treat unless stated otherwise. Statistical tests will be two-sided at the 5% significance level. Effect size estimates will be presented with 95% confidence intervals.

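### The pattern-mixture analysis misdescribes a positive β_m and, with a single β_m for the whole trial, plans no test of missingness that differs by arm

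*SAP*

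**What the plan says.** The primary analysis counts a woman with no primary outcome as smoking (SAP Section 4.4). Section 4.7.4 plans two checks on that rule: multiple imputation and a pattern-mixture model.

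The pattern-mixture model is a logistic regression with a missing-data indicator whose coefficient is β_m. The section equates β_m = −∞ with the Russell Standard. Negative values, it says, "assume that participants with missing smoking status are less likely to have quit than participants with non-missing smoking status". It continues: "while positive values assume that participants with non-missing smoking status are more likely to have quit than participants with missing smoking status". β_m is to be varied over a range that is not given and shown on a graph. No arm index or treatment-by-missingness term is mentioned.

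Two other parts of the SAP bear on this:

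- **Payments.** Since 16 March 2020, incentives women who reported having quit and "for whom a saliva sample was received by the trial team were sent a gift voucher with the value of £200" (Section 2.3.2). Before that date the £200 depended on a CO reading at or below the site threshold and on giving saliva (Section 2.3.1). Both arms receive £50 for late-pregnancy data and samples (Section 2.9.4).
- **Expected loss.** Section 2.9.4 explains the £50 as a means of limiting loss to follow-up, with controls singled out as the main worry.

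**The concern.** The two clauses on β_m say the same thing with the groups swapped, so the case in which missing women quit more often is never described. That is the half of the graph where the missing = smoking rule is challenged hardest, and someone reading it by the SAP's sentence would take it the wrong way.

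The single parameter matters more. A control who has quit gains £50 by giving a sample; an incentives woman who has quit can gain a further £200. A missing outcome may therefore hide a quitter more often in the control arm. If so, counting all missing women as smokers favours incentives. A β_m shared by the arms cannot represent that, because it shifts the log-odds of quitting among the missing by the same amount in each.

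**Working it through.** **Direction of β_m.** P(quit | missing) = expit(logit(p_obs) + β_m). At the 7% control rate of Section 2.6, logit = −2.587. β_m = +1 gives expit(−1.587) = 17.0%; β_m = −1 gives expit(−3.587) = 2.7%. Positive values make missing women more likely to have quit, which agrees with the SAP's own anchor at −∞ and contradicts its sentence.

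**The plan's own figure.** Section 2.6 states "This gave 90% power to detect a doubling of the smoking cessation rate from 7% to 14%, allowing 15% loss to follow-up", with two-sided 5% tests (Section 4.1). With p̄ = 0.105:

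n = [1.96·√(2·0.105·0.895) + 1.2816·√(0.07·0.93 + 0.14·0.86)]² / 0.07² = 401 per arm.

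401/0.85 = 472 per arm, 944 in total, against 940 planned. The figure reproduces closely, so 7%, 14% and 15% are sound starting values.

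**Equal missingness (assumed).** Take 400 of 470 observed in each arm (14.9% missing) and 33 v 66 verified quits, so that 33/470 = 7.0% and 66/470 = 14.0% under missing = smoking. The observed rates are 33/400 = 8.25% and 66/400 = 16.5%. Quits in an arm = observed quits + 70 × P(quit | missing).

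Example, controls at +1 and incentives at −∞: logit(0.0825) = −2.409; expit(−1.409) = 0.196; 33 + 70 × 0.196 = 46.7 quits. OR = (66/404)/(46.7/423.3) = 1.48. SE of log OR = √(1/46.7 + 1/423.3 + 1/66 + 1/404) = 0.203, giving 0.99 to 2.20. These Wald intervals are unadjusted and treat imputed quits as observed, so they are illustrative only.

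| β_m control | β_m incentives | Missing controls quit | Missing incentives quit | OR |
|---|---|---|---|---|
| −∞ | −∞ | 0% | 0% | 2.16 |
| 0 | 0 | 8% | 17% | 2.20 |
| +1 | +1 | 20% | 35% | 2.16 |
| +2 | +2 | 40% | 59% | 1.99 |
| +3 | +3 | 64% | 80% | 1.76 |
| 0 | −∞ | 8% | 0% | 1.82 (1.19 to 2.76) |
| +1 | −∞ | 20% | 0% | 1.48 (0.99 to 2.20) |
| +2 | −∞ | 40% | 0% | 1.10 |
| −∞ | 0 | 0% | 17% | 2.62 |

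**Unequal missingness, common β_m.** Here 7% and 14% are taken as the rates among observed women. With 20% of controls and 10% of incentives women missing:

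- β_m = −∞: 0.80 × 7% = 5.6% and 0.90 × 14% = 12.6%; OR 2.43.
- β_m = +1: 5.6% + 0.20 × 17.0% = 9.0% and 12.6% + 0.10 × 30.7% = 15.7%; OR 1.88.

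Over the same span, 25%/5% missing (control/incentives) gives 2.77 to 1.66, and 10%/20% gives 1.88 to 2.41.

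**The case against.** - **The graph can move.** A reader might infer that a common β_m hardly changes the odds ratio and would reassure whatever the truth. The documents do not support that. It holds only for similar missingness in the two arms and β_m up to about +1. The SAP's worry about controls suggests unequal loss, and then a common β_m moves the odds ratio materially. What remains is that the arms are never allowed to depart differently.
- **The effect need not vanish.** An odds ratio of 1.10 needs about 40% of missing controls to have quit, against 8% of observed controls and none of the missing incentives women. Nothing in the SAP supports those rates. Arm-specific departures can also raise the odds ratio, as the last row of the table shows.
- **The sign is a wording slip.** The anchor at −∞ and the clause on negative values fix the direction, and the computation need not change. The clause still describes the graph wrongly.
- **Equality across arms is not stated.** True; it is inferred from one parameter with no arm index. Naming the Stata command does not settle which arms are varied.
- **Other safeguards exist.** Table 9 compares sample return by arm among self-reported non-smokers, and the imputation model includes treatment allocation. Section 2.9.4 plans residual-blood testing that could show whether women lost to follow-up still smoke. The first is descriptive, and Section 4.9 carries forward only the gaming use of the blood samples. Section 4.7.6 runs opposite-arm scenarios, but only for samples not tested for anabasine.
- **Imputation model.** Late-pregnancy self-report is not among the listed predictors, which beyond the baseline covariates and allocation are "engagement with SSS, CO-validated smoking status at 4 weeks post-quit and biochemically verified point abstinence at 6 months post-partum". This is secondary. Self-reported smokers are classed as smokers without a sample, so self-report would predict the outcome perfectly in that group. Nor does Section 4.7.4 say that 4-week or 6-month values recoded to smoker enter the model.

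**Conclusion.** The point holds in two parts. The sentence on positive β_m is wrong, with consequences for reading the graph and none for the calculation. The pattern-mixture analysis, as written, tests no departure that differs by arm and states no range.

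With equal missingness of about 15%, the second part is material. The common-β_m curve stays within 2.16 to 2.20 up to +1, while a control-only departure at +1 brings the odds ratio to 1.48 with an interval that just includes 1. These figures rest on the assumed 400 of 470 observed per arm, 33 v 66 quits and an unadjusted model. The SAP gives no missingness by arm, so the true sensitivity could be smaller or larger. The primary analysis itself is unaffected. This should be changed; it does not invalidate the plan.

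**What to change.** 1. Reword the clause in Section 4.7.4: a positive β_m supposes that women whose status is missing are more likely to have quit than women whose status is known.
2. Run the pattern-mixture analysis with β_m varied in controls only, in incentives only and in both. In the one-arm runs, hold the other arm at the Russell Standard and, separately, at 0.
3. State the numerical range. Beside each β_m show the quit rate it implies among the missing in each arm, so that readers can judge plausibility, and report the β_m at which the conclusion changes.
4. Optional: use late-pregnancy self-report in the imputation. Class self-reported smokers as smokers, and impute only self-reported quitters without a sample and women not reached.

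The cost is a change of SAP wording (or an entry on the departure form named in Section 1.3.2) and a few extra model runs on data already collected. The drawback is a wider and less favourable sensitivity range.

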2.7 Randomisation

Participants were allocated using a 1:1 allocation ratio to either intervention or control using random permuted blocks with randomly varying block sizes. No stratification factors were used when randomising the participants.

To try to prevent participants in the incentives arm using the timing of the primary outcome to 'game' the study and falsely obtain the final incentives voucher, all participants were randomly assigned a date for primary outcome follow-up between 34 and 38 weeks gestation, which was calculated using the participant's EDD.

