2.9.4 Follow-up 4: Late pregnancy (34-38 weeks gestation)

All participants were followed up at the primary outcome stage in late pregnancy. Follow-up telephone contact was attempted by the trial contact centre at a random date between 34 and 38 weeks gestation allocated at the time of initial randomisation. Trial research nurses reviewed participants' notes one week prior to the telephone contact to check the health status of mother and baby and alert TCC staff to any adverse events e.g. miscarriage or stillbirth, that required particular sensitivity when conducting follow-up. TCC staff were blind to group allocation.

Three attempts were made by the TCC to contact women. If no contact was established, local research staff followed up women by telephone, text, and letter. On successful contact, women were asked: 'Have you smoked in the last 8 weeks?' If yes, 'Have you smoked more than 5 cigarettes in that time?'. EQ-5D-5L data, and current NRT/electronic cigarette use were also collected at this time point.

Self-report of not smoking was corroborated by cotinine estimation on saliva or urine (when saliva collection could not be tolerated). Where women were using NRT or e-cigarettes, anabasine assay on saliva was also conducted. Cotinine and anabasine were assayed by ABS Laboratories Limited (https://www.acmgloballab.com/about-us/our-locations/europe-london-uk). To minimise the potential for women to 'game' the primary outcome, incentive payments were dependent on the CO result, which is an immediate measure, and not on the cotinine or anabasine level.

An important aspect of the primary outcome for this phase III trial is the proportion of women successfully followed up in both the intervention and control group. To minimise loss to follow-up, particularly among controls, women in both groups will receive Love2Shop vouchers of £50 and £25 for providing data and saliva/urine samples where applicable at the primary (late pregnancy) and secondary (six months post-partum) outcome time points respectively (Figure 2.).

To assess if a) women lost to trial follow-up are still smoking towards the end of pregnancy, and b) the primary outcome has been 'gamed' (saliva cotinine below the cut-off but still smoking in late pregnancy) residual blood from routine late pregnancy samples, where available, will be tested.

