4.4 Primary outcome analysis

The primary outcome will be analysed using a mixed-effects logistic regression model adjusting for treatment group, age, years of smoking, income status (as measured by the IMD quintile within the participant's nation), level of smoking (as measured by the Fagerström score) and whether the primary outcome was collected before the 16th of March

2020 (the date on which the intervention changed due to the Covid-19 pandemic), with centre as a random effect.

For a small number of participants in Belfast, a biochemical sample was provided but due to a miscommunication with the lab the sample was not analysed for anabasine. It was decided with the TSC that in this scenario, those who self-reported as quit and had a CO reading less less than 4 ppm would be classed as non-smokers for the primary analysis.

If a participant is missing data on the primary outcome, it shall be assumed the participant is smoking, as per the Russell Standard [9]. If a participant is missing data on any covariates to be included in the analysis models, the missing values will be replaced with centre-specific means [10]. The assumptions of the model will be checked. If the assumptions are found to be questionable, the data will be transformed or non-parametric data analysis methods will be used.

It was considered whether sparse data bias would be an issue when conducting the primary analysis [11]. Given the sample size calculation assumption that 7% of participants in the control group would quit, it can be assumed that if the full sample size of 940 are recruited and the intervention has no effect, then the 'event' of a participant quitting smoking at the late pregnancy stage would be expected to occur approximately 66 times during the study. The primary analysis model contains five fixed effect variables, which means approximately 13 events per variable are expected. This exceeds the recommended minimum of 10 events per variable when using logistic regression and as a result it was not considered necessary to use an alternative statistical model [12].

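### The pattern-mixture analysis in SAP 4.7.4 gives positive β_m the wrong meaning and does not pre-specify departures that differ by arm

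*SAP*

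**What the plan says.** The primary analysis (SAP 4.4) counts a missing outcome as smoking: "If a participant is missing data on the primary outcome, it shall be assumed the participant is smoking". SAP 4.7.4 examines this rule in two ways: multiple imputation, and a pattern-mixture model run with a named Stata command.

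The pattern-mixture model is a logistic regression of the outcome on covariates and "a missing data indicator, whose parameter shall be denoted as" β_m. Minus infinity is equated with the primary rule. Negative values are correctly described as lower quitting among the missing. The section then states that "positive values assume that participants with non-missing smoking status are more likely to have quit than participants with missing smoking status". β_m is to be varied and the results graphed. No numerical range is given, and neither an arm-specific parameter nor a one-arm scenario is mentioned.

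On follow-up, SAP 2.9.4 offers vouchers to both arms for data and samples, £50 of it in late pregnancy: "To minimise loss to follow-up, particularly among controls". SAP 2.3.1 and 2.3.2 give only incentives women a further £200 voucher at that stage.

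**The concern.** The sentence on positive values repeats the direction of the negative case with the two groups swapped. A reader who relied on it would misread the positive side of the graph: a result that weakened at positive β_m would be credited to the wrong assumption about the missing women.

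The second point is about coverage. A treatment comparison is most exposed when missing women differ from observed women in one way in one arm and in another way in the other. That is plausible here, because the late-pregnancy reward for reporting a quit and giving a sample differs by arm. A usual-care woman who has quit has less to gain from responding, although the £50 paid to both arms narrows the difference. If both arms are always shifted together and missingness is similar, the shifts largely cancel in the odds ratio, and the graph says little about the departures that matter most.

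**Working it through.** **Sign of β_m.** P(quit | missing) = expit(logit(P(quit | observed)) + β_m). At minus infinity this is 0, which is the plan's anchor. It rises with β_m, equals the observed rate at 0 and exceeds it above 0. Positive values therefore mean more quitting among the missing. The plan's sentence says the reverse.

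**Inputs from the SAP.** Size (2.6): "The aim was to recruit 940 participants to the trial (470 per arm"). Design (2.6): "90% power to detect a doubling of the smoking cessation rate from 7% to 14%, allowing 15% loss to follow-up". Allocation (2.7): "Participants were allocated using a 1:1 allocation ratio". Testing (4.1): "Statistical tests will be two-sided at the 5% significance level".

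*Check on the plan's own figure.* The pooled-variance formula for 7% v 14% at 90% power gives 401 per arm; 400.95/0.85 = 471.7, so 472 per arm and 944 in total against the stated 940. The sample size is not at issue.

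**Assumptions.** The split of missingness by arm is not in the SAP; 15% in each arm is used first, then 10% incentives and 20% usual care. Observed rates of 14% v 7% are the design rates; 12% v 7% is an assumed smaller effect. Results are unadjusted.

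**Formulas, per arm** (observed rate p, missing fraction m, n = 470):

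- q = expit(logit(p) + β); arm rate π = (1 − m)p + mq
- Var(π) = [(1 − m) + m·q(1 − q)/(p(1 − p))]² · p(1 − p)/(n(1 − m)) + (q − p)² · m(1 − m)/n
- SE² of the log odds ratio = sum over arms of Var(π)/[π(1 − π)]²

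This delta-method variance gives no credit for outcomes that were not observed.

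**Common β_m, 15% missing in each arm**

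| β_m, both arms | 12% v 7%: OR (95% CI) | 14% v 7%: OR, p |
|---|---|---|
| minus infinity | 1.80 (1.11–2.92) | 2.14, p = 0.0017 |
| 0 | 1.81 (1.11–2.95) | 2.16, p = 0.0015 |
| +1 | 1.79 (1.10–2.90) | 2.13, p = 0.0017 |
| +3 | 1.53 (1.03–2.26) | 1.73, p = 0.005 |

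**Arm-specific β_m, 15% missing in each arm**

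- 12% v 7%, incentives at minus infinity, usual care at 0. Incentives: 0.85 × 0.12 = 0.102. Usual care: 0.070. OR = (0.102/0.898)/(0.070/0.930) = 1.51. The variance terms are 0.0232 and 0.0385, so SE = 0.248 and the 95% CI is 0.93–2.46 (p = 0.098). Against the primary rule this adds 470 × (0.070 − 0.0595) = 4.9 quitters in usual care.
- 14% v 7%, incentives at minus infinity, usual care at +1. Incentives: 0.85 × 0.14 = 0.119. Usual care: q = 0.170, π = 0.0595 + 0.15 × 0.170 = 0.0850. OR = (0.119/0.881)/(0.0850/0.915) = 1.45, 95% CI 0.91–2.33 (p = 0.12). This adds 470 × (0.0850 − 0.0595) = 12.0 quitters in usual care. At usual care +0.5 the OR is 1.64 (p = 0.041), so significance is lost between +0.5 and +1.

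**Unequal loss, 10% incentives and 20% usual care, common β_m**

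- 12% v 7%: 2.04 (1.25–3.33) at minus infinity, 1.81 (1.11–2.97) at 0, 1.58 (0.97–2.57) at +1.
- 14% v 7%: 2.43 (p = 0.0003) at minus infinity, 1.88 at +1, 1.70 (p = 0.026) at +1.5, 1.51 (p = 0.07) at +2. Arm-specific minus infinity v +1 already gives 1.46 (p = 0.12).

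**The case against.** The strongest reply is that the plan's method can work as it stands, and several stronger readings do fail.

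- *A reader might infer that a common β_m can never find a tipping point.* The unequal-loss results show otherwise: at 12% v 7% with 10% and 20% loss, significance is gone by +1. The near-flat curve belongs to similar missingness in the two arms.
- *A reader might infer that the plan excludes arm-specific departures.* It does not. The model is written generically and its implementation is left to a command. The text supports only that they are not pre-specified.
- *A reader might infer that the plan expects heavier loss in usual care.* SAP 2.9.4 describes a measure to reduce such loss. That non-responding usual-care women include more unverified quitters is inference, not a fact in the document.
- *A reader might infer that the sign slip itself makes the result look robust.* The anchor and the negative case fix the direction of the model. The slip harms interpretation, not the calculation.
- *A reader might infer that this is the plan's main check on the missing-data rule.* Two methods are listed and neither is called main.

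What survives is narrower. The multiple imputation carries no departure parameter. SAP 4.7.6 does use opposite assumptions by arm, but only for samples not tested for anabasine. SAP 2.9.4 plans residual-blood tests in women lost to follow-up, but SAP 4.9 reports those samples only for gaming. No section supplies arm-specific departures for missing primary outcomes.

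**Conclusion.** Both defects stand. The sentence on positive β_m is wrong by the section's own definition; this is certain from the text. The lack of pre-specified arm-specific departures, and of any stated range, follows from a literal reading.

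The size depends on assumptions. With 15% missing in each arm, a common β_m from minus infinity to +1 moves the odds ratio by no more than 0.03 at either pair of rates, while arm-specific departures equivalent to about 5 or 12 extra usual-care quitters take the lower limit below 1. Missingness by arm and the 12% rate are assumed, and the odds ratios are unadjusted illustrations. The primary analysis itself is unaffected. What is at stake is how far the sensitivity analysis can support it.

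**What to change.** In SAP 4.7.4:

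1. Correct the sentence so that positive β_m means that women with missing smoking status are more likely to have quit than women whose status is known.
2. State that β_m will be varied in incentives only, in usual care only and in both arms together, over a range fixed in advance (for example minus infinity through 0 to +1 or beyond).
3. Report the arm-specific values at which the 95% confidence interval first includes 1, alongside the number missing in each arm.

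The cost is SAP wording and a few extra model runs. The downside is that one curve becomes three.
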